#### 4.2 Secondary endpoints:

4.2.1 Assessment of FI severity by the Fecal Incontinence Severity Scale (FISS) which is derived from the Fecal Incontinence and **Constipation Assessment** questionnaire. This is a validated FI severity scale which incorporates the frequency of different types of stool loss (solid, liquid, staining and a combination), the circumstances surrounding FI (urgency, passive, combined, or neither), and volume of leakage. It is the only scale that incorporates the volume of leakage. which the NIDDK Workshop recommended be included when evaluating the severity of FI. The originally published scale will be adapted for use as an outcome measure by changing the reporting period for symptoms to the past month rather than the past year. The psychometric properties of this instrument have been validated in community-based studies, and it has been used in a therapeutic trial . Symptom severity ranked by this

### Table 2: Measurements Table for FIT Study\*

Schedule of assessments	Screening	Baseline	Randomize	3 mo	6 mo	12 mo	18 mo	24 mo
Socio-demographics and examination	X							
Bowel diary, including BSFS		X	x	X	X	X		Х
Endoanal ultrasound		X**		X*** (INJ arm only)				
Balloon Evacuation Test (BET)		X**						2 X
Anorectal manometry (ARM)	08	X**		X***		2 2		
Magnetic Evoked Potential (MEP)		X**		X***		2		
Fecal Incontinence Severity Scale (FISS)		х	х	X	X	X		Х
Fecal Incontinence Quality of Life (FIQOL)	2	x	x	X	X	X		Х
PHQ-12 Somatization scale			x	x	X	x		X
PROMIS Anxiety-7			X	Х	X	X		Х
PROMIS Depression-8			X	X	X	Х		Х
PROMIS Self-Efficacy Symptom Management			Х	X	x	X		Х
Assessment of AEs, SAEs		Х	х	Х	X	X	x	Х
Cost (treatments, # of visits, out of pocket)		X	X	X	X	X	х	X
Work Productivity and Impairment (WPAI)	95 	X	x	Х	X	Х	x	Х
EuroQol 5D (EQ-5D)		X	X	Х	X	Х	Х	Х
Burden of Treatment Questionnaire		x	X	X	X	Х	X	Х
GI Symptom Questionnaire		X						
ABLe			X	X	X	Х		Х
Continence Rating			X	Х	X	Х		Х

\* Additionally, participants will complete the Credibility/ Expectancy Questionnaire (CEQ) each time that they start one of the four study interventions (EMM, BIO, INJ and SNS). So, all study participants will complete the CEQ when they start EMM and all randomized participants will complete the CEQ when they start BIO, INJ or SNS either as a randomized treatment or if they select BIO, INJ or SNS when they are identified as non-responders to the randomized treatment at the 3-month follow-up assessments.

\*\* The endoanal ultrasound, BET, ARM and MEP may be conducted at the randomization visit, if not done at Baseline. If an imaging study (US or MRI) was performed in the previous 12 months to assess the sphincters, then this need not be repeated at Baseline if the sphincters appeared normal and there has been no history of anorectal trauma, surgical procedures, or vaginal deliveries in the intervening period between the imaging exam and study participation.

\*\*\*The endoanal ultrasound (INJ only), the ARM (all participants) and the MEP (all participants) may be performed at the 3-month follow-up assessment. Participants who complete two 3-month follow-up visits should only have the ARM and MEP performed at the first 3-month follow-up visit. This will only apply to participants who initially respond to EMM but are later identified as non-responders at the 3-month follow-up visit and are then randomized to BIO or INJ. They will complete another 3-month follow-up visit, this time three months after they have initiated one of the randomized treatments. NOTE: Participants who elect to receive INJ as an optional treatment may have an endoanal ultrasound at their follow-up visit following completion of that treatment (likely their 6-month follow-up visit).

scale is strongly correlated with the impact of FI on quality of life. It will be given at baseline, end of EMM, 3, 6, 12, and 24 months (Table 2).

*4.2.2 Fifty percent responder*. To facilitate comparisons with previously published studies that have used a 50% responder definition, we will also calculate the proportion of patients who have at least a 50% reduction in FI episodes. This will be calculated from diary data entered in the EDC system at the end of EMM and at 3-, 6-, 12-, and 24-month follow-up.

4.2.3 Continence rating. The proportion of patients in each treatment arm who are continent at each follow up will be reported as an additional secondary outcome of treatment efficacy. This will be calculated from diary data entered in the EDC system at the end of EMM, and at 3, 6, 12, and 24 months. Continence will be defined by three criteria: (1) Absence of FI episodes on the two-week bowel diary, (2) self-report by the patient using a questionnaire that they have had no ABLs for the last month, and (3) self-report that they "no longer have this problem" (question 1 below).

- 1. Have you had any ABLs in the last 30 days? Yes/No.
- "How would you rate your response to this treatment? Please choose from the following: (a) Worse than before treatment. (b) About the same as before treatment. (c) Somewhat improved. (d) Much improved. (e) I no longer have this problem."

*4.2.4 FI Quality of Life (FIQOL) scale*. This is a validated disease-specific quality of life scale which is commonly used in FI treatment trials. It will be given at baseline, end of EMM, and 3, 6, 12, and 24 months follow up (Table 2). The FIQOL contains 29 items and is scored for four subscales: Lifestyle, Coping/Behavior, Depression/Self-Perception, and Embarrassment. It has good convergent validity with generic measures of health-related quality of life, good test-retest reliability, and ability to discriminate patients with FI from those with IBS.

4.2.5 PROMIS Anxiety Scale. PROMIS refers to the Patient Reported Outcomes Measurement Information System, which is a large collection of publicly available outcome measures available to clinical researchers. This library of validated patient reported outcome scales resulted from a collaboration between academic investigators and the National Institutes of Health. A team of PROMIS investigators consisting of experts in each domain (including anxiety) identified candidate items from existing questionnaires and wrote new items when necessary. This large item bank was then reviewed and revised if necessary, tested in focus groups of patients and non-patients to ensure domain coverage, and tested for understandability by cognitive interviews with individual items. Final edits were then made prior to field testing in large samples drawn from the population and from clinical samples. For each domain, a large bank of items was developed to be used as a pool of items for future test development, and subsets of items were selected for the development of computer adaptive testing (CAT) based on item response theory, and short paper forms of (typically) 4-8 items. Although there are no publications listed in PubMed for the use of the PROMIS Anxiety Scale in patients with FI, there are data on the psychometric properties of the scales in population samples and clinical samples with other disorders such as cancer and knee osteoarthritis. These sources show that the 7-item PROMIS anxiety scale correlated .97 with the 29 items in the full bank of anxiety items, showed an alpha reliability coefficient of .98 throughout most of the range for the scale, and a correlation of .96 with legacy measures of anxiety. In clinical samples of patients with knee osteoarthritis and multiple sclerosis, the correlations with legacy measures of anxiety were .71 and .95 respectively.

*4.2.6 PROMIS Depression Scale.* This scale was developed by the same process as the PROMIS Anxiety scale above. The 8-item short form PROMIS Depression scale correlates .96 with the whole bank of 28 depression items, has a reliability coefficient of .99 through most of the range of scores, and is correlated .83 with the CES-D depression scale. In clinic samples with knee osteoarthritis and multiple sclerosis, the correlations are .70 and .80 respectively.

4.2.7 PROMIS Self-Efficacy for Managing Symptoms Scale. This questionnaire was developed to assess the participant's willingness to engage in self-management skills, which is relevant to how patients perceive and react to the obligation to learn new skills and practice them when managing a symptom as compared to
accepting a treatment applied by a physician that does not require any responsibility for self-management. Although no validity data has been reported for the self-efficacy scale, this scale was selected because the items have face validity for FI (example: "I can keep my symptoms from interfering with relationships with friends and family." )

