- C. Identify baseline predictors of responsiveness to each intervention and the mechanistic basis for each treatment. Candidate predictors are (a) demographic variables (e.g., sex, age, race, ethnicity, education); (b) clinical history variables (e.g., FI frequency, volume, duration, and association with urgency and diarrhea); and (c) baseline pelvic floor physiology (e.g., anal canal resting pressure, squeeze pressure, duration of squeeze, rectal sensory threshold for first sensation and urgency, maximum tolerable volume, structural integrity of anal sphincters assessed by ultrasound, and integrity of the pelvic floor innervation by trans-sacral and trans-lumbar magnetic evoked potentials).

- D. Evaluate treatment combinations. Patients who do not meet the responder criterion by 3 months follow up will be offered the option of choosing additional therapy. This constitutes a pragmatic clinical trial which mimics clinical practice and will provide preliminary data for a future study. A second reason for allowing patients to add an additional preferred treatment if they do not show at least a 75% improvement is to facilitate recruitment; in our feasibility survey, subjects told us that the opportunity to try another treatment if the first failed would increase their willingness to be randomized. Data analysis will estimate 95% confidence intervals for the percent of responders to each treatment combination and to each monotherapy, and differences in responder rates between groups will be assessed.
  - Research objective 4. To compare the improvement in FI after combination treatment versus monotherapy and compare improvement among various treatment combinations, up to 24 months after administration of each treatment combination, compared to monotherapy.
  - Research objective 5. To estimate differences in the magnitude of improvement in FI from baseline to end of treatment between the treatment combinations.
- E. Assess the efficacy and durability of enhanced medical treatment and identify patient characteristics that predict treatment response.
  - Research objective 6. To estimate the responder rate during the last two weeks of enhanced medical treatment and also during follow up at 3, 6, 12, and 24 months.
  - Research objective 7. To assess the proportion of patients reporting AEs of pelvic pain of grade II or higher, or SAEs requiring hospitalization, during all weeks of medical treatment.

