- 8. Characterization of Enhanced Medical Treatment Durability of improvement and predictors of response: The primary purpose of treating all patients with an EMM run-in is to be able to exclude patients who do not require more costly interventions. However, we will take advantage of the opportunity provided by this run-in study to identify predictors of response to EMM and to assess the durability of improvements. EMM will not be "usual care" but will follow a written protocol that is intended to optimize EMM, which is why we label this enhanced medical management. Patients who are treatment responders at the end of the EMM run-in will be scheduled for 3-month follow-up, and those who are no longer treatment responders at 3 months follow up will be offered an opportunity to be randomized to one of the 2 treatments at this point. However, those who remain responders to EMM at 3 months follow up will continue to be followed for an additional 21 months. All patients, regardless of their outcomes at the end of EMM, will be encouraged to continue using the treatment approaches learned during the EMM phase. Participants, whether determined to be EMM responders or not, will be asked at the end of the 1-month EMM period and then also at the 3-; 6-; 12-; and 24-month follow-up assessments if they are continuing to adhere to these treatment approaches (pelvic floor exercises and medication).

Event	Window for event
Screening	N/A
Baseline	To be completed no more than 6 weeks after Screening Visit.
EMM – start	EMM should start 0 days – 4 weeks from the completion of the Baseline diary.
EMM - Check-in Calls	
 
Call 1: 3 – 5 business days after starting EMM
 
14-day call: 2 business days before - 2 business days after the 14th day from the start of EMM
 

Randomization in Medidata	Randomization in Medidata EDC should occur 4 weeks - 6 weeks after the start of EMM. Note :
	
 
The Randomization Visit may occur anytime between the end of EMM and Treatment Initiation.
 

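### The 30-day continence question is longer than the 28-day EMM run-in, so the end-of-EMM continence rate is biased downward, depends on visit date and is not comparable with later visits

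*Combined protocol and SAP*

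**What the plan says.** Section 4.2.3 requires all three of the following for a participant to count as continent:

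1. a clean diary, given as "Absence of FI episodes on the two-week bowel diary";
2. a dry month by the participant's own account, given as "self-report by the patient using a questionnaire that they have had no ABLs for the last month", which the questionnaire puts as "Have you had any ABLs in the last 30 days? Yes/No";
3. a global rating that the problem is gone.

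On timing it states: "This will be calculated from diary data entered in the EDC system at the end of EMM, and at 3, 6, 12, and 24 months". It gives no separate rule for the end of EMM. Table 2 schedules the "Continence Rating" row first in the Randomize column and then at 3, 6, 12 and 24 months.

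Section 3.0 sets EMM at 4 weeks. Section 3.1 says that randomization "in Medidata EDC should occur 4 weeks - 6 weeks after the start of EMM" and lets the Randomization Visit fall at any point from the end of EMM until treatment starts. Section 5.1 requires an average of at least 2 FI episodes per week during the two-week baseline.

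The companion EMM measure uses a shorter period. Research objective 6 in Section 1.1 is "To estimate the responder rate during the last two weeks of enhanced medical treatment", and again at each follow-up.

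**The concern.** A 30-day look-back cannot fit inside a 28-day treatment. At an assessment close to the end of EMM, the question asks whether the participant was dry from the first day of EMM or from before it. It does not ask whether they are dry now that EMM has had time to work. Someone who leaked in week 1 and was then completely dry for the last two weeks passes the diary criterion and fails the 30-day one.

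From 3 months on, the same 30 days lie well after treatment began, so the same definition measures something different. A low continence percentage at end of EMM followed by a higher one at 3 months could then come from the look-back alone. The end-of-EMM percentage would also move with how promptly sites schedule the visit.

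**Working it through.** The plan states no expected end-of-EMM continence rate, so there is no figure to reproduce. The check is date arithmetic followed by an illustrative model.

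**Inputs.** Look-back 30 days (Section 4.2.3). EMM 28 days (Section 3.0). Randomization on day 28 to 42 after EMM start (Section 3.1). Pre-treatment rate at least 2 episodes per week (Section 5.1). For higher rates, Table 3 gives 3.4 and 4.8 FI days per week in the two pivotal trials; using these as episodes per week is an assumption.

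**Dates.** With EMM starting on day 0 and assessment on day *d*, the look-back begins on day *d* − 30.

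- Day 28: 28 − 30 = −2. It covers all of EMM plus 2 untreated days.
- Day 29: all of EMM plus 1 untreated day.
- Day 30: exactly from the start of EMM.
- Day 35: from EMM day 5, so 23/28 = 82% of EMM.
- Day 42: from EMM day 12, so 16/28 = 57% of EMM.
- The look-back clears the first two weeks of EMM only from day 14 + 30 = 44.

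At 3 months (taken as 90 days) the earliest permitted assessment is 1 week early, so the look-back begins about 90 − 7 − 30 = 53 days after Time 0. For EMM responders, Time 0 is the date the randomization eligibility form is completed.

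**Model.** Take a participant who is dry on EMM days 14 to 28 and so has a clean diary. Let episodes be Poisson with rate *r* per week before EMM. After EMM starts, the rate drops to zero at once, or falls linearly to zero over *R* = 7 or 14 days. With *p* = max(0, 30 − *d*) untreated days and *s* = max(0, *d* − 30), the expected episodes in the look-back are

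*m* = *rp*/7 + (*r*/7)(*R* − *s*)²/(2*R*),

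where the second term is zero if *s* ≥ *R* or if the effect is immediate. The chance of passing the 30-day item is exp(−*m*).

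Worked case, *r* = 2, *R* = 14:

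- Day 28: *m* = 2 × 2/7 + (2/7) × 14²/28 = 0.571 + 2 = 2.571, and exp(−2.571) = 0.076.
- Day 42: *m* = (2/7) × 2²/28 = 0.041, and exp(−0.041) = 0.960.

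Chance of passing, at *r* = 2 / 3.4 / 4.8 per week:

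| Assessment day | Immediate effect | 7-day fall | 14-day fall |
|---|---|---|---|
| 28 | 57 / 38 / 25% | 21 / 7 / 2% | 8 / 1 / 0.2% |
| 30 | 100% | 37 / 18 / 9% | 14 / 3 / 1% |
| 35 | 100% | 92 / 87 / 82% | 44 / 25 / 14% |
| 42 | 100% | 100% | 96 / 93 / 91% |

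**Who can be reclassified.** Participants randomized straight after EMM have less than a 75% reduction, so they still have episodes on the diary and already fail the first criterion. That leaves EMM responders, expected to be 57 of 285 (Section 5.4; 57/285 = 20%), and among them only those with no episodes in 14 days. The documents do not say how many that would be.

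**The case against.** The strongest reply is that little rests on this number. Section 8.3 analyses the efficacy and durability of EMM through response rates at the end of EMM and at 3, 6, 12 and 24 months, and continence is not part of that analysis. Section 8.2 models continence at the follow-up time points, without formal testing and with p-values for information only. No planned analysis contrasts EMM continence at end of treatment with 3 months. All of this stands. A reader might infer that the Aim E durability result is distorted, but the documents do not support that. What remains is a percentage that Section 4.2.3 says will be calculated and that would mislead if set beside later ones.

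It can also be said that a month without leakage is a deliberately strict standard, and that 14 dry days need not count as continence. That is a fair choice from 3 months on. At the end of EMM the same rule also asks about days before treatment or before it had taken hold, so it is no longer the same standard. The mismatch between a 14-day response and a 30-day continence period exists at every visit and is not itself a fault of the EMM time point.

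Finally, the day 28 to 42 window governs randomization in the data system and not the Randomization Visit. Treatment may start up to 4 weeks after randomization, so the visit could fall as late as day 42 + 28 = 70. No day-42 limit is stated for EMM responders, who are not randomized at that point. It would therefore be wrong to infer that the look-back always includes the first two weeks of EMM. This flexibility narrows the bias for late visits, but it is also why the rate depends on visit date.

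**Conclusion.** The point holds in a limited form. As written, the end-of-EMM continence rate is biased downward, strongly when assessed near day 28 and little by day 42. It depends on the visit date and is not comparable with the rates at 3, 6, 12 and 24 months.

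A reader might go further and infer that the rate is driven towards zero. The modelled pass rates run from 0.2% to 100%, depending on visit day, baseline rate and speed of onset. They are near zero only for assessments close to day 28 to 30 with a gradual effect. The date arithmetic rests on the documents alone; the percentages rest on the Poisson and linear-fall assumptions and are illustrative.

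The reach is small: a subset of about 57 expected responders among 285, in a descriptive secondary outcome. The planned EMM responder-rate analysis and the randomized comparison of biofeedback with injection are untouched. It is worth correcting mainly because the correction costs so little.

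**What to change.** Amend Section 4.2.3 and the continence paragraph of Section 8.2 as follows:

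- Report diary-only continence (no FI episodes on the 14-day diary) at end of EMM and at 3, 6, 12 and 24 months, and name this as the series for comparison across time points.
- Do not apply the 30-day item at end of EMM. Keep the three-criterion definition from 3 months on.
- Tidy two related statements in Section 4.2.3. It says continence is calculated from diary data, although two of the three criteria are questionnaire items. It also points to question 1 for the global rating, although question 1 is the 30-day item.

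The cost is wording only, because Table 2 already schedules the bowel diary at each of these time points. The downside is that the end-of-EMM figure will be less strict than the three-criterion figure at later visits. Only the diary-only series should therefore be compared over time, and the report should say so.

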## 4.3 Moderator variables

*4.3.1 PHQ12 (Somatization).* This scale is derived from the Prime MD structured interview. It consists of the 15 most commonly reported symptoms in primary care practice. The subject is asked to rate how much they were bothered by each symptom in the last 1 months on a scale from 0="not bothered at all" to 2="bothered a lot". Total scores are 0-30, with cut-off points of 5, 10, and 15 dividing the responders into mild, medium, and high severity. The PHQ-15 is highly correlated with other measures of somatization, and it is a strong predictor of disability days, clinic visits, and scores on all subscales of the SF-20 health related quality of life scale. Cronbach's alpha is .80. The PHQ-15 includes 3 gastrointestinal symptoms, which could confound the interpretation of the impact of somatization in gastrointestinal (GI) disorders if the GI symptoms on the PHQ-15 are part of the diagnostic criteria for the GI disorder. Spiller has recommended eliminating these three items for GI studies, and he refers to this derived scale as the PHQ-12. The cut-points dividing mild, medium, and high severity will be adjusted to 4, 8, and 12. We are using the PHQ-12 as a moderator variable because we have found somatization (measured by a different scale) to be a strong predictor of fecal incontinence severity. This is included as a moderator variable because recent unpublished studies show that somatization is a strong predictor of FI-specific quality of life.

*4.3.2 Credibility/expectancy questionnaire (CEQ)*. A potential bias in trials where the treatment conditions cannot be masked is the patient's perception of the credibility and expectation of benefit associated with the treatments; these have been shown to influence the outcome of clinical trials. It is possible to assess the extent of this bias by asking patients to rate the intervention to which they are randomized for credibility and expectancy after their first exposure to the treatments. The CEQ consists of 6 items which are scored for two subscales: credibility and expectancy. This questionnaire has high internal consistency and good test-retest reliability. It is recommended to be used in clinical trials of behavioral and surgical interventions where it is not possible to mask which treatment subjects are receiving and where a priori differences in credibility and expectancy could confound the interpretation of the trial results.

This questionnaire will be completed each time the participant starts one of the study interventions (EMM, BIO, INJ), as well as the optional treatment, SNS. So, all participants should complete the CEQ at least once – when they begin EMM. Randomized participants will complete it once or twice more – when they begin the randomized treatment (BIO, INJ) and then possibly again if they are identified as non-responders to the randomized treatment at the 3-month follow-up assessment and select the other treatment to which they were not originally randomized or SNS. The CEQ should always be administered at the treatment initiation visit but **after** the treatment has been initiated as follows:

- EMM after the participant has completed the EMM treatment initiation session;
- BIO after the participant has completed the TRAIN 1 session;
- INJ after the participant has received the injection of bulking agent;
- SNS after the participant has undergone the procedure to implant the temporary leads.

*4.3.3 Sex*. Because there are different risk-factors for FI in females vs. males, it is possible that the females and males will respond differently to these treatments. Randomization will be stratified by sex.

*4.3.4 Subtype of FI:* Passive vs. urge-related FI. Passive FI is defined as FI that occurs without any warning sensation, while urge FI is said to occur when the patient feels a warning sensation of rectal fullness or urgency prior to stool leakage but is unable to reach the toilet before leakage occurs. It has been suggested that dextranomer may be more effective in patients with passive FI as compared to urge FI. Patients will be classified at baseline as passive FI if their symptom diary shows >50% of FI episodes occurring without warning and as urge FI if <50% occur without warning.

*4.3.5 Bristol Stool Form Scale (BSFS) rating of stool consistency*. This is imbedded in the bowel diary. Measured at baseline, end of EMM, and at 3-, 6-, 12-, and 24-month follow-up (Table 2). The bowel diary form

includes validated pictures and descriptors of 7 different stool consistencies. For each 14-day bowel diary, we will compute the proportion of all BMs (including both continent and incontinent BMs) that are rated as BSFS types 1 or 2, and the proportion rated as BSFS types 6 or 7. The BSFS is a valid measure of stool form which correlates more strongly with whole gut transit time measured by the radio-opaque marker technique (r=.54) than with stool frequency (r=.35) or total stool output (r=.41). BSFS rating are also responsive to treatment with laxatives or antidiarrheal medications. Another study showed a significant correlation of r=.49 between the BSFS ratings of healthy volunteers and stool water content, and a stronger correlation of r=.70 between BSFS ratings made by GI experts and stool water. As might be expected from the classification of a continuous measure into discrete categories, there is moderate variability between raters in the discrimination of type 2 from type 3 and the discrimination of type 5 from type 6, but there is excellent discrimination overall between the three functional categories: hard stools of types 1-2, normal stools of types 3-5, and loose stools of types 6-7.

4.3.6 Anorectal manometry. Determine anal resting and anal squeeze pressures, sphincter squeeze endurance, rectal sensory thresholds (bag volume and intra-bag pressure at the first report of sensation, desire to defecate, urgency to defecate, and maximum tolerable volume), and rectal compliance. These parameters will be measured at baseline (but can be measured prior to randomization if not measured at Baseline) and may also be done at 3 months following initial treatment using the portable Medspira Anorectal manometry equipment, which can be used in the office and does not require a dedicated laboratory. This system includes a catheter, with 4 radially-oriented equidistant anal balloons and 1 rectal balloon, a wireless manometer, and a computer. The catheter is connected to the manometer that has pressure transducers and communicates wirelessly to the computer. The acquisition module display provides instructions that guide users conducting the study. The maneuvers used during portable manometry are identical to those in high-resolution manometry (HRM). Anorectal pressures and rectal sensation measured with portable manometry are significantly correlated with high-resolution manometry. Participants who initially respond to EMM but are then randomized after they are identified as non-responders at the 3-month follow-up visit may have the ARM performed at the initial 3-month assessment but it should not be repeated at their second 3-month follow-up assessment if they are then randomized to BIO or INJ.

4.3.7 Motor evoked potentials (MEP) will be tested at the Baseline visit (but can be tested at any time before randomization). It may also be tested at 3-month follow-up in all treatment groups. However, participants who initially respond to EMM but are then randomized after they are identified as non-responders at the 3-month follow-up assessment will not have the MEP repeated at their second 3-month follow-up assessment, that is, at the follow-up 3 months after they initiated the randomized treatment. The MEP data will be collected at the Mayo Clinic and Augusta University. MEP data will not be collected at the University of North Carolina at Chapel Hill, the University of Alabama at Birmingham, and the University of Michigan.

This test uses a specially designed rectal probe with 2 pairs of bipolar steel ring electrodes, each 2 cm apart, mounted on a catheter (Gaeltec Ltd, Isle of Skye). The proximal pair will be located 8-10 cm from anus and the distal pair at 1-2 cm from anus. The electrodes are used to record the motor evoked potentials after magnetic stimulation. Magnetic stimulation of the lumbar (TLMS) and sacral (TSMS) nerve roots will be performed using a commercially available 90 mm coil magnetic stimulator (Magstim 200^2; MAGSTIM, Whitland, UK). The subject will lie prone. For the TLMS study, the coil will be placed on each side of the midline approximately 3-5 cm laterally and between L2 and L3 vertebra. The coil will be discharged with increasing frequency starting at 50% and up to a maximum output of 85% of the scale range for magnetic stimulation intensity. For the TSMS test, the sacrum will be palpated to identify the S2 and S3 vertebra. The coil will be placed on each side of the midline over the sacrum (S2-S3) and discharged up to a maximum of 85% magnetic stimulation intensity. The EMG responses from anterior tibialis muscle of one leg will also be recorded (as a control) using Ag/AgCl disc electrodes The MEP responses will be recorded into a 4-channel amplifier with a built in AD interface (Nihon Kohden, Japan) with filter settings of 5-2000 Hz and at a sampling rate of 4-8 kHz, fed into a computer for display and analysis. Figure 3 shows the whole system. An optimal response will be defined as an anal and rectal MEPs of >10µV and tibialis response of 100µV on at least 3/6 consecutive trials. A rest period of 5 minutes will be allowed between stimulations on each side. Five MEP responses will be obtained on each side and the average of the best three responses will be used to measure MEP response.

Measurements and Analysis: The latencies of wave forms (Figure 2) on both the TLMS and TSMS-induced MEP responses will be analyzed on both the right and left sides. The first and most prominent negative or positive deflection will be designated as the MEP response. We will measure the average latency for the left lumbo-rectal and lumbo-anal and the right lumbo-rectal and lumbo-anal MEPs. Similarly, the average latency for the left sacro-rectal and left sacro-anal and the right sacro-rectal and right sacro-anal MEP responses will be measured for a total of 8 measures. Each averaged response latency will be classified as abnormal if it is greater than the upper confidence interval reported previously for healthy controls; otherwise normal. Patients will be classified as having a neuropathy if  $\geq$ 1 of 8 average latencies are abnormal. The validity of this test as a measure of pelvic nerve neuropathies was demonstrated in previous studies showing that these latencies differentiate patients with FI as a group from healthy controls (abnormally delayed latencies in 80% of patients with FI), and abnormally delayed latencies are also found in patients with spinal cord injury (known neuropathy)

Figure 2. Typical motor response to magnetic stimulation of the lumbar spine

4.3.8 Anorectal ultrasound or pelvic floor MRI. Measured at baseline (but if not done at Baseline, can still be measured up to and including at the time of the Randomization visit) in all subjects and may also be done at 3 months in dextranomer treated patients. Sites will report who performs and interprets the test, whether an anorectal ultrasound or a pelvic floor MRI was performed, the person performing the test and the person interpreting the study, the width of any defects in the internal and external anal sphincters and puborectalis muscles, and the minimum thickness of these muscles. For sites using anorectal ultrasound, BK probes that are 3 dimensional will be used, except for The University of Alabama at Birmingham where 2 dimensional BK probes will be used. Please see the Anorectal ultrasound/pelvic floor operating procedure manuals. If this was performed in the previous 12 months to assess the sphincters, then this need not be repeated at Baseline if the sphincters appeared normal and there has been no history of anorectal trauma, surgical procedures, or vaginal deliveries in the intervening period between the imaging exam and study participation.

4.3.9 Treatment Burden Scale. This questionnaire was developed to assist in understanding the burden of treatment, concerning time needed to complete the treatment, risk of new symptoms, adverse events or side effects, personal responsibility, and financial burden of the treatment.

